#### STUDY DESIGN

Two-arm, cluster randomized controlled trial comparing two approaches for outreach presentations for caregivers about evidence-based practices for youth anxiety. One presentation will be facilitated by a researcher and a key opinion leader (KOL; KOL condition), and the other one facilitated by two researchers (researcher-only condition). Neither the researchers nor the participants are blinded to study condition.

#### STUDY AIMS AND HYPOTHESES

This study will use a mixed methods approach (integrating quantitative and qualitative methods) to test the effect of KOLs on increasing caregiver demand for CBT for youth anxiety through the following aims:

## **Primary Aims**

**Aim 1:** Test the relative effects of researcher-only and KOL conditions on changing caregivers' intention to seek CBT for their youth, and actual CBT seeking at three-month follow up.

*Hypothesis 1a:* Relative to the researcher-only condition, the KOL condition will result in a greater increase in intention to seek CBT with exposures.

*Hypothesis 1b:* Relative to the researcher-only condition, the KOL condition will result in a greater seeking of CBT with exposures for their youth at the three-month follow-up.

## **Secondary Aims**

**Aim 2:** Test the relative effects of researcher-only and KOL conditions on changing caregivers' (a) perceived subjective norms about seeking CBT, (b) attitudes about CBT, (c) stigma about mental illness, and (d) knowledge of how to seek EBPs.

*Hypothesis 2a:* Relative to the researcher-only condition, the KOL condition will result in a greater (a) increase in subjective norms about seeking CBT, (b) attitudes about CBT, and (c) decrease in caregiver stigma about mental illness.

*Hypothesis 2b:* Both presentation conditions will result in a similar increase in knowledge about how to seek EBPs.

**Aim 3:** Examine how KOLs affect participants' impression of the researcher presenter. **Hypothesis 3:** Participants will view the principal investigator (i.e., the first author) more favorably when she presents with the KOL, relative to when she presents with another researcher.

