#### Criteria for exclusion:

None

**Sample size:** For aim 1 and 3, a Monte Carlo-based power estimate was derived using Mplus with 10,000 replications. For the sample size of 180, assuming a Type I error rate of 5%, a two-tailed test, statistical power was .83 to detect a medium-sized effect (r = .30) of randomization group on longitudinal changes, given an expectation of a small (r = .15) effect for the control group. For aim 2, power was calculated using G\*Power. Given the brevity of the three-month follow-up questionnaire, a 10% attrition rate was assumed. Assuming a Type I error rate of 5%,

a two-tailed test, and a 25% rate of seeking EBPs in the researcher-only condition, statistical power was .82 to detect a medium effect (odd ratio = 1.72).

**Randomization:** Participants will be cluster randomized by school using restricted randomization with Excel's random number generator.

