#### Secondary outcome measures:

3. Change From Pre-Presentation to Post-Presentation in Parent Engagement in Evidence-Based Services Questionnaire, Knowledge Subscale [Time Frame: pre-presentation; post-presentation (within 1 week after the presentation)]

The Parent Engagement in Evidence-Based Services Questionnaire, Knowledge subscale (PEEBS-K) assesses caregiver perceived understanding of how to seek evidence-based practice (Chang et al., 2019). Participants rate five items on a ranging

from 1 (*strongly disagree*) to 5 (*strongly agree*). Items are summed; higher scores indicate higher levels of perceived knowledge about seeking evidence-based practice.

4. Change From Pre-Presentation to Post-Presentation in Therapy Subjective Norms Questionnaire [Time Frame: pre-presentation; post-presentation (within 1 week after the presentation)]

The Therapy Subjective Norms Questionnaire is a six-item measure of caregiver perception of subjective norms for seeking therapy. It was modeled from previously used measures of subjective norms (Glanz et al., 2008; Park & Smith, 2007). Items are rated on a scale ranging from 1 (*strongly disagree*) to 7 (*strongly agree*). Items are summed; higher scores indicate more positive subjective norms about seeking therapy.

5. Change From Pre-Presentation to Post-Presentation in Caregiver Attitudes About Cognitive Behavioral Therapy [Time Frame: pre-presentation; post-presentation (within 1 week after the presentation)]

The Caregiver Attitudes about Cognitive Behavioral Therapy includes 18 strategies used in cognitive behavioral therapy for youth anxiety. Participants rate how helpful they believe each strategy would be for treating their child on a five-point scale ranging from 1 (*very unhelpful*) to 5 (*very helpful*). Items are summed; higher scores indicate more favorable attitudes.

6. Change From Pre-Presentation to Post-Presentation in Parents' Internalized Stigma of Mental Illness Scale [Time Frame: pre-presentation; post-presentation (within 1 week after the presentation)]

The Parents' Internalized Stigma of Mental Illness Scale (PISMIS) assesses caregiver perception of internalized stigma for having a youth with a mental illness (Zisman-Ilani et al., 2013). Participants rate each statement on a scale ranging from 1 (*strongly disagree*) to 4 (*strongly agree*); some items are reverse scored. Items are summed; higher scores indicate higher levels of family stigma.

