researcher co-facilitator) as a person-level predictor; and time (pre- and post-presentation) as an observation-level predictor. In separate multilevel models, (a) intention to seek CBT, (b) Therapy Subjective Norms Questionnaire—CBT, (c) Caregiver Attitudes about CBT, (d) Parents' Internalized Stigma of Mental Illness Scale, and (e) Parent Engagement in Evidence-Based Services Questionnaire-Knowledge subscale will be regressed on time, condition, and the interaction between time and condition; a random intercept will be included in all five multilevel models. A binary logistic regression will be conducted with CBT service seeking at the threemonth follow-up (Treatment Seeking Evaluation - Actual CBT seeking) entered as the dependent variable, condition entered as the independent variable, and youth anxiety (Brief Revised Child Anxiety and Depression Scale-Total Anxiety) entered as a control variable. Ttests will be used to compare difference between conditions for each item on the Relatability Evaluation of the principal investigator. This study will examine caregiver demographic factors, youth anxiety (Brief Revised Child Anxiety and Depression Scale-Total Anxiety), racial similarity to the presenter (Demographics, same race), and self-disclosure (Content Checklist, selfdisclosure), as potential moderators of the effect of presentation condition on intention to seek CBT. In separate multilevel models, intention to seek CBT will be regressed on time, condition, each potential moderators, and their three-way interaction.

**Qualitative Analyses:** The transcribed qualitative interviews will be entered into NVivo software for analysis. Qualitative analyses will use a direct content analysis approach (Hsieh & Shannon, 2016). The coding team will create an initial codebook using the primary topics asked in the qualitative interviews. Additional codes will be added to code text that does not fit into the initial categories, either to split the initial codes into two, or to create new codes. Coding will occur through a consensus process in which each transcript will be coded independently by two raters, who will arrive at consensus through discussion (Hill et al., 2005). Thematic responses will be examined by both condition and by whether the caregiver has sought treatment for their youth (4 groups total).

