**Integration Procedures:** Mixed methods integration will follow a QUAN → qual structure with an expansion approach (Palinkas et al., 2010); quantitative methods being used to test hypotheses about the intervention and qualitative methods being used to contextual the results.

**Data collection at the time of the SAP:** As of 8/11/21, pre/post presentation data has been collected from 17 participants. Three-month follow-up data has not yet been collected. No data has been analyzed.

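### Hypothesis 2b predicts a similar knowledge gain in both arms, but the only planned between-arm analysis is a difference test, which can contradict similarity but cannot establish it

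*Combined protocol and SAP*

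**What the plan says.** Secondary Aims contains two kinds of hypothesis. Hypothesis 2a predicts a difference: "Relative to the researcher-only condition, the KOL condition will result in a greater (a) increase in subjective norms about seeking CBT", with matching predictions for attitudes and stigma. Hypothesis 2b predicts the absence of one: "Both presentation conditions will result in a similar increase in knowledge about how to seek EBPs".

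Planned Analyses does not carry that distinction through. Intention, subjective norms, attitudes, stigma and knowledge each get a separate model in which the outcome "will be regressed on time, condition, and the interaction between time and condition", and "a random intercept will be included in all five multilevel models". The moderator models concern intention only, so the time-by-condition term is the only planned between-arm comparison of knowledge change.

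The outcome is the five-item PEEBS-K, each item rated 1 to 5: "Items are summed; higher scores indicate higher levels of perceived knowledge about seeking evidence-based practice". On allocation, the plan says: "Participants will be cluster randomized by school using restricted randomization".

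The sample size paragraph gives a total of 180 and power for detecting differences. The figure it labels as aim 2 concerns the rate of seeking treatment (25%, odds ratio 1.72), so no power statement covers knowledge. Neither that paragraph nor the statistical analysis plan contains an equivalence margin, an interval criterion or a rule for reading a non-significant interaction.

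**The concern.** Hypothesis 2b has two parts. The time terms address whether knowledge increases. Whether the increase is similar across arms is left to a test whose null hypothesis is no difference. Rejecting that null contradicts 2b. Failing to reject it shows only that the data did not exclude zero, and they may not exclude a difference that matters either.

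The plan does not say that non-significance will be taken as similarity. It does not rule that reading out, though, and it plans no other evidence. The risk is a reported finding that the two presentations conveyed knowledge equally well, resting on an interaction that was merely non-significant.

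**Working it through.** **Inputs.** From the plan: total N = 180; two-sided 5% test; knowledge score range 5 × 1 = 5 to 5 × 5 = 25; randomisation by school. Not in the plan, so assumed: allocation, number and size of schools, the ICC of change, and any margin. The SD of change is not given either, so all differences are in units of that SD. The plan states no figure for hypothesis 2b, so there is none to reproduce.

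**1. How often a real difference is missed (no clustering).**

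SE = √(1/n₁ + 1/n₂); at 90/90 this is √(2/90) = 0.149.

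P(non-significant | δ) = Φ(1.96 − δ/SE) − Φ(−1.96 − δ/SE).

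- δ = 0.2: δ/SE = 1.342, so Φ(0.618) − Φ(−3.302) = .731
- δ = 0.3: δ/SE = 2.012, so Φ(−0.052) − Φ(−3.972) = .479

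| Arms | SE | δ = 0.2 | δ = 0.3 |
|---|---|---|---|
| 90/90 | 0.149 | .731 | .479 |
| 120/60 | 0.158 | .756 | .525 |
| 81/81 | 0.157 | .753 | .520 |

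The 81/81 row applies a 10% loss. The plan states that rate for the three-month follow-up and gives none for the pre-to-post interval, so the row is illustrative.

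**2. What an equivalence rule could deliver.** Two one-sided 5% tests are the same as requiring the 90% CI to lie inside ±M. With a true difference of zero and no clustering, power = 2Φ(M/SE − 1.645) − 1:

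- M = 0.5: 2Φ(1.709) − 1 = .913
- M = 0.4: 2Φ(1.038) − 1 = .701
- M = 0.3: 2Φ(0.367) − 1 = .287

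The margin giving 80% power is (1.645 + 1.282) × 0.149 ≈ 0.44 SD.

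**3. The same rule with clustering.** This is a cluster-level analysis of change with K equal schools of m, split evenly between arms. The variance of a school mean is ICC + (1 − ICC)/m, and the t reference has K − 2 df. For K = 12, m = 15 and ICC = .05, the variance is .05 + .95/15 = .1133 and SE = √(2 × .1133/6) = 0.194. The 90% CI half-width is 1.812 × 0.194 = 0.352 SD. Powers by simulation with an estimated SE:

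| Schools × size | ICC of change | M = 0.5 | M = 0.4 | M = 0.3 |
|---|---|---|---|---|
| 12 × 15 | .02 | .73 | .44 | .13 |
| 12 × 15 | .05 | .55 | .26 | .05 |
| 18 × 10 | .05 | .69 | .38 | .08 |
| 6 × 30 | .05 | .26 | .12 | .04 |

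For 12 × 15 with ICC .05, 80% power needs a margin of about 0.61 SD.

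**4. Which model the interval may come from.** With complete pre/post pairs, a school random intercept cancels out of each caregiver's change. For 12 × 15 with change variance 1, the generalised least squares SE of the interaction is 0.1491 with no school term. It is still 0.1491 with a school intercept variance of .05, .15 or .40. It rises to 0.1944 with a school-by-time variance of .05. The plan's three-level fallback with only a random intercept therefore leaves this SE unchanged.

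When the true difference equals the margin (12 × 15, ICC .05), a 90% CI without a school-by-time term declares equivalence in about 10% of simulated trials at margins of 0.5 and 0.4 SD. The cluster-level interval with 10 df does so in about 4–5%, against a nominal 5%.

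**The case against.** The strongest reply is that the planned model already yields an estimate and standard error for the interaction, and a narrow interval around zero would say something about similarity. Aim 2 is worded neutrally, as a test of relative effects, and the interaction estimates exactly that. The word 'similar' may have been meant informally, and the plan nowhere states that a null result will be read as equivalence.

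Much of this is fair. The model can stay, and the same coefficient serves the remedy. What is missing is a criterion fixed in advance: without one, almost any interval could be called similar afterwards. If the word is meant descriptively, the plan can say so in a sentence. But 2b is a labelled hypothesis under a testing aim, beside 2a's directional predictions, and a reader will expect the analysis to decide it.

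It can also be said that the clustering material applies to all five outcomes and that the equivalence powers rest on unknown inputs. Both are true. Clustering matters here because an equivalence claim from too narrow an interval errs towards declaring similarity. The wide range of powers is a reason to make the equivalence rule optional.

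**Conclusion.** The concern holds. The stated analysis does not match the stated hypothesis: it can refute similarity but gives no basis for concluding it. That follows from the form of the test and needs no assumption about sample size.

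The size does rest on assumptions. In the unclustered layouts examined, a true difference of 0.2 SD of change is non-significant about 73–76% of the time, and one of 0.3 SD about 48–53%. The consequence is confined to one secondary hypothesis. It should nevertheless be corrected, because following the plan as written invites reading a null result as similarity.

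**What to change.** **Minimum change.** Before any analysis, state that the between-arm part of hypothesis 2b is an estimation question: the time-by-condition estimate will be reported with its confidence interval, and no claim of similarity will be drawn from non-significance. This is one sentence and needs no margin. When the SAP was written, pre/post data were in hand from 17 participants and the plan records "No data has been analyzed", so the change could still have been made in advance.

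**Optional equivalence rule.** If the sponsor can justify a margin, give it in points of the 5–25 score, set it without looking at the pre/post data already collected, and conclude similarity only if the 90% CI lies wholly within it. Take that interval from a model with a school-by-time random effect, or from a cluster-level analysis of change scores with small-sample degrees of freedom. The cost is a defensible margin, an analysis the plan does not now contain, and a real chance of an inconclusive result at margins of 0.5 SD or tighter once clustering is allowed for.

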#### **PARTICIPANTS**

#### Criteria for inclusion:

- Be least 18 years of age
- Be fluent in English
- Be the primary caregiver of a youth aged 5 to 18 years
- Have a child at one of the schools offering a presentation

#### Criteria for exclusion:

None

**Sample size:** For aim 1 and 3, a Monte Carlo-based power estimate was derived using Mplus with 10,000 replications. For the sample size of 180, assuming a Type I error rate of 5%, a two-tailed test, statistical power was .83 to detect a medium-sized effect (r = .30) of randomization group on longitudinal changes, given an expectation of a small (r = .15) effect for the control group. For aim 2, power was calculated using G\*Power. Given the brevity of the three-month follow-up questionnaire, a 10% attrition rate was assumed. Assuming a Type I error rate of 5%,

a two-tailed test, and a 25% rate of seeking EBPs in the researcher-only condition, statistical power was .82 to detect a medium effect (odd ratio = 1.72).

**Randomization:** Participants will be cluster randomized by school using restricted randomization with Excel's random number generator.

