### **Exploratory outcome measures:**

- 7. Change From Pre-Presentation to Post-Presentation in Barriers to Seeking Treatment [Time Frame: pre-presentation; post-presentation (within 1 week after the presentation)]

  The Barriers to Seeking Treatment questionnaire asks participants to indicate whether they agree with 21 potential barriers to treatment (Heeringa et al., 2004). A count of the total number of barriers will be used in analyses.
- 8. Change From Pre-Presentation to 3-Month Follow-Up in Barriers to Seeking Treatment [Time Frame: pre-presentation; 3-month follow-up]

The Barriers to Seeking Treatment questionnaire asks participants to indicate whether they agree with 21 potential barriers to treatment (yes/no; Heeringa et al., 2004). A count of the total number of barriers will be used in analyses.

9. Client Satisfaction Questionnaire [Time Frame: post-presentation (within 1 week after the presentation)]

The Client Satisfaction Questionnaire assesses participants' satisfaction with the presentation. Items are rated on scale ranging from 1 to 4. Items are summed; higher composite scores indicate greater program satisfaction.

10. Relatability Evaluation [Time Frame: post-presentation (within 1 week after the presentation)]

The Relatability Evaluation will be used to evaluate participants' impression of the presenter. Participants will rate each presenter (scale ranging from 1 to 5) on 10 items associated with aspects of key opinion leaders: relatable, likeable, similar, think similarly, similar beliefs, credible, trustworthy, understanding of the local community, familiar, and friendship. Items are summed; higher composite scores indicate that the presenter is more relatable.

11. Brief Revised Child Anxiety and Depression Scale-Parent Version [Time Frame: prepresentation]

The total anxiety scale (15 items) from the Brief Revised Child Anxiety and Depression Scale-Parent Version will be used to assess youth anxiety (Ebesutani et al., 2017). Participants rate items on a scale from 0 (*never*) to 3 (*always*). Items are summed; higher scores indicate higher levels of anxiety.

12. Demographics [Time Frame: pre-presentation]

A demographics questionnaire will assess caregiver and youth age, gender, race, ethnicity, and nativity; caregiver level of education, income, and religion; and youth health insurance status.

13. Content Checklist [Time Frame: during the 1.5 hour presentation]

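### The sample-size paragraph pairs its power calculations with the wrong aims: .83 does not describe Aim 3, and the seeking-rate calculation labelled Aim 2 fits only Hypothesis 1b

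*Combined protocol and SAP*

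**What the plan says.** The Sample size paragraph (Participants section) gives two calculations and ties each to numbered aims.

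- **Aims 1 and 3.** "For aim 1 and 3, a Monte Carlo-based power estimate was derived using Mplus with 10,000 replications". Its inputs are "For the sample size of 180, assuming a Type I error rate of 5%, a two-tailed test". Its result is "statistical power was .83 to detect a medium-sized effect (r = .30) of randomization group on longitudinal changes". The control arm is assumed to show a smaller effect, r = .15.
- **Aim 2.** A G\*Power calculation, introduced by "For aim 2, power was calculated using", takes 10% attrition at the three-month questionnaire, a 25% rate of seeking EBPs in the researcher-only arm, an odds ratio of 1.72 and power of .82.

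The other sections define the aims as follows.

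- **Aim 1** (Primary Aims) has two parts: change in intention to seek CBT (Hypothesis 1a) and actual seeking at three months (Hypothesis 1b).
- **Aim 2** (Secondary Aims) covers norms, attitudes and stigma (Hypothesis 2a) and knowledge (Hypothesis 2b, a similar increase in both arms). Secondary outcome measures lists all four as summed scales taken before and after the presentation.
- **Aim 3** (Secondary Aims) is to "Examine how KOLs affect participants' impression of the researcher presenter". Its measure is listed as "10. Relatability Evaluation [Time Frame: post-presentation (within 1 week after the presentation"; no earlier rating is scheduled. Planned Analyses compares the principal investigator's ratings between conditions by a t-test for each item.

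**The concern.** Each power statement should describe the endpoint, visits and test of the aim it is attached to. Here three pairings fail.

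1. Aim 3 carries a power for longitudinal change, but its rating has one time point.
2. Aim 2 carries a power for a yes/no outcome at three months, but its outcomes are pre/post scale scores.
3. Hypothesis 1b, a primary outcome, falls by its label under the longitudinal calculation, which does not describe a single yes/no outcome.

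A reader would judge a null result on Hypothesis 3 against an 83% figure derived for a different kind of endpoint. For Aim 2 the reader would find only a calculation about treatment seeking. Nothing elsewhere in the document corrects the labels.

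**Working it through.** **1. Match each calculation to the endpoints**

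| Hypothesis | Endpoint and visits | Planned test | Calculation by label | Calculation that fits |
|---|---|---|---|---|
| 1a | Intention, pre and post | Time-by-condition multilevel model | Mplus, .83 | Mplus |
| 1b | Sought CBT yes/no, 3 months | Logistic regression | Mplus, .83 | G\*Power type |
| 2a | Norms, attitudes, stigma, pre and post | Time-by-condition multilevel model | G\*Power, .82 | Mplus |
| 2b | Knowledge, pre and post, similar increase | Time-by-condition multilevel model | G\*Power, .82 | Neither |
| 3 | Relatability items, post only | t-test per item | Mplus, .83 | Neither |

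**2. Can .83 be reproduced?** Not uniquely, because the Mplus population model is not given. Variants at N = 180, two-sided 5%, with 90 per arm assumed:

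- Fisher z, r = .30 against 0 in all 180: .98.
- Fisher z, r = .30 against .15 in two independent arms of 90: .18.
- Change scores. Convert by d = 2r/√(1 − r²): r = .30 gives 0.629 and r = .15 gives 0.303, a difference of 0.326. The change-score SD is √(2(1 − ρ)), with ρ the pre-post correlation, and power = Φ(0.326/(SD·√(2/90)) − 1.96). This gives .59, .80 and .93 at ρ = .5, .7 and .8, and .83 at ρ of about .72.

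So .83 is attainable as a pre/post figure under an unstated correlation. It can be neither confirmed nor refuted.

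**3. Power of Aim 3's planned comparison.** Two-sample t-test, 90 per arm assumed, noncentrality d·√(90/2).

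- r = .30, d = 0.629: noncentrality 4.22, power .99.
- d = 0.50: power .92.
- Power of .83 needs d of about 0.44.

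Allowing for schools, replace 90 by 90/DE, with DE = 1 + (m − 1)·ICC. Neither m (caregivers per school) nor the ICC is in the documents, so both are assumed. At d = 0.629:

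| m | ICC | DE | Effective n per arm | Power |
|---|---|---|---|---|
| 10 | .01 | 1.09 | 82.6 | .98 |
| 10 | .05 | 1.45 | 62.1 | .94 |
| 10 | .10 | 1.90 | 47.4 | .86 |
| 20 | .01 | 1.19 | 75.6 | .97 |
| 20 | .05 | 1.95 | 46.2 | .85 |
| 20 | .10 | 2.90 | 31.0 | .68 |

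Degrees of freedom here come from effective caregivers, not schools, which favours the plan.

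**4. Does .82 hold once moved to Hypothesis 1b?**

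- Odds in the KOL arm: 1.72 × .25/.75 = 0.573, so the rate is 0.573/1.573 = 36.4%.
- Analysed number: 180 × 0.90 = 162, or 81 per arm.
- SE of the log odds ratio: √(1/(81 × .25 × .75) + 1/(81 × .364 × .636)) = 0.345.
- Power: Φ(ln 1.72/0.345 − 1.96) = Φ(0.542/0.345 − 1.96) = .35.
- At 90 per arm the same formula gives .38 (.39 from the unpooled difference in proportions).

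Treating the predictor as a standard-normal variable gives .80 at N = 162 and .84 at N = 180. That comes close to .82, but condition is a two-level factor.

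**The case against.** The strongest reply is that the aim numbers have simply been mislabelled and little depends on it. The longitudinal calculation describes the design that Aim 2 uses, and the seeking-rate calculation plainly belongs to three-month seeking. Aim 3 is secondary and its measure is listed as exploratory. At r = .30, the group effect the paragraph names, Aim 3's power is .99 unclustered and exceeds .83 in five of the six clustered scenarios above.

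Most of this stands, and it limits the point. Relabelling does not remove it, however: Aim 3 would still have no calculation, Hypothesis 2b would have none suited to a claim of similarity, and .82 would be attached to a primary outcome that it does not fit.

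A reader might go further and infer that Aim 3 is underpowered, or that no power can exist for it. The documents support neither. A two-sample t-test has a power once an effect size is chosen, and the plan chooses none. Nor can the r = .15 in the paragraph serve as a pessimistic between-arm effect for Aim 3, because the text gives it as the expected effect in the control group.

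**Conclusion.** The pairing is wrong as written, and the documents state no applicable power for Aim 3. Because .83 cannot be rebuilt from the stated inputs, this is a finding about what the figure is attached to, not a demonstrated error in the figure itself.

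Aim 3's power is a range: .99 at d = 0.63 without clustering, and about .68 to .98 under the assumed ICCs and school sizes. It rests on equal arms of 90 and on carrying r = .30 over to a between-arm difference, which the plan does not do. The three-month interview also asks about perception of presenters, but it is qualitative and not a repeated score, so it does not supply the missing longitudinal change.

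The consequence for Aim 3 is modest. The larger numerical gap appears when the G\*Power calculation is placed where it belongs: about .35 against the stated .82 for Hypothesis 1b.

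**What to change.** Rewrite the Sample size paragraph by hypothesis rather than by aim.

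- Assign the Mplus calculation to Hypotheses 1a and 2a, and state the pre-post correlation and variance structure it used.
- Remove the .83 claim for Aim 3. State the power of the post-only, per-item t-tests with an explicit effect size, the arm sizes and a range of school ICCs. Power for the composite score would not match the planned per-item analysis.
- Assign the G\*Power calculation to Hypothesis 1b, but recompute it for a two-group comparison first. Do not carry .82 over unchanged.
- Do not apply a power to detect a difference to Hypothesis 2b. Either give a margin and a matching calculation, or say that the hypothesis is descriptive.

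The cost is one rewritten paragraph and two short calculations, with a third if a margin is set for Hypothesis 2b. No change to the design or data collection is needed. The downside is that the restated figures depend on assumed effects and ICCs and may be less favourable.

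### The power of .82 stated for three-month CBT seeking, a primary outcome, does not follow from its own inputs; a two-arm comparison on those inputs has power of about .35

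*Combined protocol and SAP*

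**What the plan says.** The Sample size paragraph under PARTICIPANTS contains two calculations.

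- The first, by Mplus simulation for Aims 1 and 3, carries the only sample size given: "For the sample size of 180, assuming a Type I error rate of 5%, a two-tailed test, statistical power was .83".
- The second, by G*Power, is labelled Aim 2. It states "Given the brevity of the three-month follow-up questionnaire, a 10% attrition rate was assumed", then "a two-tailed test, and a 25% rate of seeking EBPs in the researcher-only condition" at a 5% type I error rate, and concludes "statistical power was .82 to detect a medium effect (odd ratio = 1.72".

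The second calculation concerns a rate of seeking at three months expressed as an odds ratio. That is Hypothesis 1b under Aim 1, which expects that "the KOL condition will result in a greater seeking of CBT with exposures for their youth at the three-month follow-up". The MEASURES section lists it as the second primary outcome, answered yes or no. Aim 2 covers norms, attitudes, stigma and knowledge, so the label appears to be a slip.

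Planned Analyses specifies a binary logistic regression of seeking on condition, which has two levels, with youth anxiety as a covariate. The paragraph does not give the G*Power settings, the allocation ratio or any allowance for randomization by school.

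**The concern.** An odds ratio of 1.72 on a 25% base rate is a difference of about 11 percentage points. A two-arm trial of fewer than 200 people cannot detect that with power above .80.

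The figure is the only statement of what the trial can show on actual treatment seeking. At a true power of .35, the trial would miss the assumed effect about 65% of the time, not 18%. A non-significant result could then be taken as fair evidence against the KOL approach when the test had little chance of finding the effect. The error does not bias the estimate or alter the type I error; it misstates how informative the result will be.

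**Working it through.** **Inputs.** From the Sample size paragraph: 180 participants, 10% attrition, two-sided 5%, control rate 25%, odds ratio 1.72, stated power .82. From STUDY DESIGN: two arms. Assumed: the 180 applies to this calculation, giving 180 × 0.9 = 162 completers, and allocation is equal, giving 81 per arm.

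**KOL-arm rate.** Control odds = .25/.75 = .3333. KOL odds = .3333 × 1.72 = .5733. Rate = .5733/1.5733 = .364.

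**Power, Wald test on the log odds ratio.**
- ln(1.72) = .542
- SE = √[1/(81 × .25 × .75) + 1/(81 × .364 × .636)] = √(.0658 + .0533) = .345
- Power = Φ(.542/.345 − 1.96) = Φ(−.39) = .35

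**Power, two-proportion z test with pooled null variance.**
- Difference = .1144; mean rate = .307
- Null SE = √(2 × .307 × .693/81) = .0725; alternative SE = √[(.1875 + .2316)/81] = .0719
- Power = Φ[(.1144 − 1.96 × .0725)/.0719] = Φ(−.385) = .35

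Simulation also gives .35. The stated .82 is not reproduced.

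**Other two-arm readings.**

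| Reading | Power |
|---|---|
| All 180 analysed | .38 |
| One-sided test, N = 162 | .47 |
| 2:1 or 1:2 allocation, N = 162 | .30 to .33 |
| 180 per arm; 162 per arm | .65; .61 |
| 1.72 as a risk ratio (25% v 43%), N = 162; N = 180 | .68; .73 |
| Any control rate from 5% to 95%, 81 per arm | at most about .40 |
| With anxiety covariate (assumed OR per SD 1 to 4; conditional OR 1.72) | .34 falling to .26 |

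**What .82 would require.**
- At OR 1.72: n per arm = [1.96 × √(2 × .307 × .693) + .915 × √(.1875 + .2316)]² / .1144² = 3.50/.01309 ≈ 268, or 536 completers in total.
- At 81 per arm: an odds ratio of about 2.61 by the two-proportion test (25% v 46.5%), or about 2.66 by the Wald test.

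**A possible source of .82.** If condition is entered as a continuous standard-normal predictor with 1.72 per SD, the Hsieh approximation at N = 162 gives Φ[√(162 × .1875) × .542 − 1.96] = Φ(1.03) = .85. The Demidenko formula gives .80, or .84 with variance correction, and simulation gives .82. The logistic routine may therefore have been run with a normal rather than a two-level predictor. The documents do not give the settings, so this is an inference.

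**Clustering.** The number of schools and the ICC are not given. Assuming 10 schools (16.2 completers each), the design effect is 1 + 15.2 × ICC. That is 1.30 at ICC .02, with power about .28, and 1.76 at ICC .05, with power about .22.

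**The case against.** The case on the other side does not dispute .35 on these inputs. It makes four points about what surrounds that number.

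- **Derived inputs.** The 162 and the equal split are not in the document, and 180 is attached to the other calculation. This is correct, and both should be labelled as assumptions. Neither rescues .82: across N = 162 to 180 and the unequal splits, power stays between .30 and .38.
- **Another route to .82.** Reading 1.72 as a risk ratio, with a one-sided test and all 180 analysed, gives .82. So the normal predictor is not the only possible explanation, and it should stay a conjecture. But this route contradicts three stated inputs: the odds ratio, the two-tailed test and the attrition.
- **Effect-size label.** OR 1.72 converts to d = .542 × √3/π = .30 and r ≈ .15, a value the same paragraph calls small. That label, however, describes the expected effect in the control group in a longitudinal model. The mismatch appears only after a conversion the plan does not use, so it is a side point.
- **Not the planned test.** The .35 is unadjusted and unclustered, whereas the plan adjusts for anxiety and randomizes schools. This is true, and any replacement figure should say so. Both features lower power in the scenarios tried, so .35 is, if anything, generous.

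**Conclusion.** The concern holds. On the paragraph's own control rate, odds ratio, error rate and attrition, a two-arm comparison has power of about .35, less than half the stated .82. This rests on applying 10% attrition to 180 and on equal arms, and it ignores clustering and the covariate. The conclusion is not sensitive to the first two assumptions, and the last two push power lower in the scenarios tried. No two-arm reading that keeps the stated odds ratio and two-tailed test reaches .82. The error is in a central design figure for a primary outcome and should be corrected. How it arose is not established and does not affect the conclusion.

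**What to change.** Replace the sentence with one of the following.

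- With about 162 completers in equal arms, power is about .35 for an odds ratio of 1.72 (25% v 36.4%), two-sided 5%, unadjusted and before any school design effect.
- With the same N, test and caveats, the odds ratio detectable with power of about .82 is about 2.6 (25% v about 46.5%).

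State the N, allocation, test and software settings, and relabel the calculation as Aim 1, Hypothesis 1b. If the number of schools is known, add power over a range of ICCs.

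Two optional improvements: drop the word *medium* for an odds ratio of 1.72, and present Hypothesis 1b mainly through the odds ratio and its confidence interval. At an SE of about .345, the 95% limits are the estimate divided and multiplied by exp(1.96 × .345) ≈ 1.97. An estimate of 1.72 would run from about 0.87 to 3.4 before clustering.

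The cost is wording and a less favourable stated power; enrolment need not change. The SAP records that no three-month data had been collected and nothing analysed as of 8/11/21, so a correction made at that stage could not be influenced by results.
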